7.3.4 Safety analyses

Adverse events will be coded using the Medical Dictionary for Drug Regulatory Activities (MedDRA). Standard BI summary tables and listings will be produced. All adverse events with an onset between start of treatment and end of the REP, a period of 42 days after the last dose of trial medication, will be assigned to the on-treatment period for evaluation. As the treatment arms are made up of a combination of individual treatments a patient may have multiple last doses of treatment; therefore the last dose of study medication is defined as the latest of these.

All treated patients will be included in the safety analysis, according to the actual trial medication they received. In general, safety analyses will be descriptive in nature and will be based on BI standards. No hypothesis testing is planned.

Statistical analysis and reporting of adverse events will concentrate on treatment-emergent adverse events, i.e. all adverse events occurring between start of treatment and end of the residual effect period. Adverse events that start before first drug intake and deteriorate under treatment will also be considered as ‘treatment-emergent’.

Frequency, severity, and causal relationship of adverse events will be tabulated by system organ class and preferred term after coding according to the current version of the MedDRA at the database lock.

Laboratory data will be analysed both quantitatively as well as qualitatively. The latter will be done via comparison of laboratory data to their reference ranges. Values outside the reference range as well as values defined as clinically relevant will be summarised. Treatment groups will be compared descriptively with regard to distribution parameters as well as with regard to frequency and percentage of patients with abnormal values or clinically relevant abnormal values.

Vital signs, physical examinations, or other safety-relevant data observed at screening, baseline, during the course of the trial and at the end-of-trial evaluation will be assessed with regard to possible changes compared to findings before start of treatment.

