7. PLANNED ANALYSIS

In general (unless specified elsewhere), BI standards (3) will be followed for the End-Of-Text tables. In summary:

- The set of statistics for continuous data is N / Mean / Standard Deviation / minimum (Min) / lower quartile (Q1) / Median / upper quartile (Q3) / Maximum (Max). Other than the Min and Max, all statistics will be presented to one more decimal place than the raw data.
- Tabulations of frequencies for categorical data will include all possible categories and will display the number of observations in a category as well as the percentage (%) relative to the respective treatment group (unless otherwise specified, all patients in the respective patient set whether they have non-missing values or not). Percentages will be rounded to one decimal place. The category 'missing' will only be displayed if there are actually missing values.
- Time-to-event endpoints will be summarised in months [Months = (Days x 12) / 365.25] to one decimal place. Hazard ratios (HRs) and corresponding confidence intervals (CIs) will be presented to two decimal places. P-values will be presented to four decimal places.

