7.8.1 Adverse Events

AEs will be coded with the most recent version of the MedDRA. The severity of AEs will be scaled according to Common Terminology Criteria (CTC) AE version 5.

Unless otherwise specified, the analyses of AEs will be descriptive in nature. All analyses of AEs will be based on the number of patients with AEs and not on the number of AEs.

For analysis, multiple AE occurrence data on the eCRF will be collapsed into an AE if all of the following applies:

- All AE attributes are identical (Lowest Level Term [LLT], CTCAE grade, action taken with trial medication, therapy required, seriousness, reason for seriousness, relationship, outcome, AE of special interest)
- The occurrences are time overlapping or time-adjacent (time-adjacency of 2 occurrences is given if the second occurrence started on the same day or on the day after the end of the first occurrence).

For further details on the analysis and presentation of AE data refer to BI standards [\(5\)](#).

The analysis of AEs will be based on the concept of treatment emergent adverse events. That means that all AEs with an onset between first drug intake and last drug intake + REP (42 days) will be assigned to the randomised treatment. All AEs with an onset before first drug intake will be assigned to 'screening' and all AEs with an onset after the residual effect period will be assigned to 'post-treatment' (for listings only). For details on the treatment definition, see [Section 6.1](#).

An overall summary of AEs will be presented; along with the standard categories presented additional categories for action taken and drug relationship with each compound, worst CTCAE grade and infusion related reaction response. The frequency of patients with AEs will be summarised by treatment, highest CTCAE grade, primary SOC and PT. The SOC's will be sorted alphabetically; PT's will be sorted by decreasing frequency (within SOC). Only AEs with a given CTCAE grade will be displayed in tables showing AEs by worst CTCAE grade. AEs with a missing CTCAE grade will not be displayed in these tables; a footnote will explain that these AEs are not included and a separate listing of them will be produced if required. The following tables will be produced for AEs during the on-treatment period:

- Patients with AEs
- Patients with any related AE

- Patients with related xentuzumab/placebo AEs
- Patients with related everolimus AEs
- Patients with related exemestane AEs
- Patients with SAEs

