7.8.2 Laboratory data

The analyses of laboratory data will be descriptive in nature and will be based on BI standards (6). The same on-treatment periods as considered for the analysis of AEs will be applied for laboratory values. Patients having at least one post-baseline laboratory value will be displayed in the descriptive analyses.

The focus of the laboratory data analysis will be on the following primary laboratory parameters:

- Alanine aminotransferase (ALT), aspartate aminotransferase (AST), total bilirubin, glucose, creatinine, platelets, cholesterol, triglycerides, neutrophils, lymphocytes, haemoglobin and white blood cells.

Descriptive statistics including baseline, last value on-treatment and change from baseline to last value on-treatment will be produced. CTCAE grades for applicable laboratory parameters will be calculated according to CTCAE version 5. The following outputs will be presented for each of the above parameters:

- Transitions of CTCAE grade from baseline to worst on-treatment laboratory value
- Transitions of CTCAE grade from baseline to last on-treatment laboratory value

Patients with no CTCAE grade due to missing laboratory values will be displayed as 'Missing'. Note with version 5 of the CTCAE grading some of laboratory parameters detailed above (ALT, AST and total bilirubin) can no longer be assigned a grade at baseline. For these parameters, the CTCAE shift tables will be replaced by shift tables of pre-defined categories

based on Upper Limit of Normal (ULN) values. A similar approach will also be adopted for creatinine due the ambiguity of CTCAE grading for grades 2 and 3. The pre-defined categories will follow BI standards (7).

Possible clinically significant abnormal laboratory values are defined as those laboratory values that are of CTCAE Grade ≥ 2 and show an increase from baseline value by at least one CTCAE grade. For those parameters for which no CTCAE has been defined, BI standard definition will be used to determine possible clinical significance. Frequency of patients with possible clinically significant abnormal laboratory values will be provided whenever applicable. If no baseline value is available (or CTCAE grading at baseline cannot be assigned) but the patient has a post-baseline laboratory value of CTCAE Grade ≥ 2 an increase from baseline will be assumed, i.e. the laboratory value considered as possible clinically significant.

Hepatic enzyme elevations (potential Hy's law cases):

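### By-grade adverse event tables omit events with no CTCAE grade, so a row can understate incidence; add an all-grades total and a missing-grade category

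*SAP*

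**What the plan says.** SAP 7.8.1 bases AE analyses on numbers of patients and sets the layout: "The frequency of patients with AEs will be summarised by treatment, highest CTCAE grade, primary SOC and PT". It then limits the content: "Only AEs with a given CTCAE grade will be displayed in tables showing AEs by worst CTCAE grade". The next sentence deals with the rest: "AEs with a missing CTCAE grade will not be displayed in these tables". It adds that the omission will be explained in a footnote and that these events will be listed separately if that is required.

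A list of on-treatment tables follows. It covers all AEs, related AEs (any drug and each drug), SAEs and related SAEs, other significant AEs, AEs leading to discontinuation, dose reduction or interruption, and AESIs. Only AEs leading to death carries a note that no grade is needed. The special search category summaries are also laid out by highest grade.

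Other parts of the plan bear on this:

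- **SAP 7**, for categorical tables in general and unless specified elsewhere: the missing category "will only be displayed if there are actually missing values", and percentages are taken over all patients in the set.
- **SAP 7.8.2**, laboratory CTCAE tables: "Patients with no CTCAE grade due to missing laboratory values will be displayed as" missing.
- **Protocol 7.3.4**: "Frequency, severity, and causal relationship of adverse events will be tabulated by system organ class and preferred term".
- **Protocol 5.2.6.1**: intensity should be recorded in the CRF under CTCAE version 5.0.
- **SAP 7.8 and 7.8.1**: an overall AE summary and registry disclosure tables are also produced. Neither is described as a by-grade table.

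**The concern.** Whether an event happened does not depend on whether its grade was entered. A by-grade table normally serves two purposes: it shows how severe the events were, and its total shows how many patients had the event at all. Under the SAP rule an ungraded event is lost to both. SAP 7.8.1 specifies neither a missing-grade column nor a total that includes ungraded events.

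What is at stake is the incidence of individual terms, and of SAEs and AESIs by term, in a small trial where single patients are visible in the percentages. A row affected in this way could also disagree with the overall AE summary, which is not described as subject to the exclusion.

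**Working it through.** The plan gives no figure to reproduce. The check is a reading of the text, followed by a small illustration.

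**Step 1: which tables the rule reaches.** The rule is worded for tables that show AEs by worst grade. The layout sentence comes immediately before it and the list of tables shortly after. One table in that list is marked as not needing a grade, which implies that the others are by grade. The special search category summaries state a by-grade layout themselves. So the rule appears to reach the listed tables other than AEs leading to death, plus the special search category summaries.

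**Step 2: what the rule does to a row.** For one arm and one row (a system organ class, preferred term or grouped term), let

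- n = treated patients in the arm,
- x = patients with at least one graded event in the row,
- u = patients whose only events in the row are ungraded.

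The incidence is (x + u)/n. The table reports x/n. The difference is

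(x + u)/n − x/n = u/n ≥ 0.

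The denominator does not change, because SAP 7 takes percentages over all patients in the set. The reported figure is therefore equal to or below the incidence, never above it. A patient with both a graded and an ungraded event in the same row is part of x and is still counted.

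**Step 3: size per patient.** The protocol synopsis plans about 40 patients per arm. Protocol 7.7 caps randomisation at 100, which is 100/2 = 50 per arm. Assuming all randomised patients are treated:

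| n per arm | Effect of one omitted patient (1/n) |
|---|---|
| 40 | 1/40 = 2.5 percentage points |
| 50 | 1/50 = 2.0 percentage points |

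The documents give no basis for a value of u. If every AE is graded, u = 0 and the effect is zero.

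**Step 4: comparison with the plan's other conventions.** The general convention in SAP 7 shows a missing category when values are missing. The laboratory CTCAE tables keep patients without a grade visible. The AE tables drop the ungraded event and move it to a footnote and a possible listing. The SAP therefore foresees ungraded AEs but handles them differently from ungraded laboratory values.

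**The case against.** A reader might infer that every AE table is by grade, and that patients with ungraded events vanish from the safety report. The documents do not support this. AEs leading to death are exempt. In the overall AE summary, worst grade is one added category among others, and the disclosure tables are produced separately. The rule removes events rather than patients, and the omission is footnoted.

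A reader might also infer that the SAP contradicts itself. It does not. The general convention applies unless specified elsewhere, and SAP 7.8.1 is such a specification. The laboratory tables are also a different object: they are shift tables with calculated grades, which need a cell for a missing value.

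The practical case for leaving the rule alone is reasonable:

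- The protocol asks investigators to grade AEs, and quality review precedes database lock.
- Safety analyses are descriptive.
- SAEs and AESIs reach the sponsor within 24 hours, and the data monitoring committee reviews safety.
- The hepatic-injury AESI is defined by laboratory thresholds, and SAP 7.8.2 tabulates the corresponding elevations from laboratory data.

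It would therefore go too far to say that a safety signal would be missed.

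All of this stands, and it limits the point to a minor one. It does not restore the by-grade counts. A footnote says that events were left out but does not put the patient back in the row, and the listing is conditional. The sponsor's AE reporting standard, which the SAP cites for further detail, was not available. What the overall summary contains is therefore read from the SAP text alone.

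**Conclusion.** The point holds as a minor reporting weakness. In the tables shown by worst grade, a patient whose only event in a row is ungraded is not counted in that row, so incidence there can only be understated. Each such patient costs 2.5 percentage points at about 40 per arm, or 2.0 at about 50.

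The total effect cannot be computed, because the number of ungraded AEs is not known in advance. It should be small, and it is zero if grading is complete. The conclusion assumes that the listed tables, other than AEs leading to death, follow the by-grade layout that SAP 7.8.1 sets out just before them. It does not extend to the overall AE summary or the disclosure tables.

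**What to change.** In SAP 7.8.1, replace the exclusion with three provisions:

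1. Every on-treatment AE counts in an all-grades total of each by-grade table, including the special search category summaries.
2. A missing-grade category is shown whenever an ungraded AE exists, in line with the laboratory CTCAE tables.
3. The listing of ungraded AEs is produced whenever there are any, rather than only if required.

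The cost is a short wording change in the SAP and an adjustment to the table shells. No new data are needed, and no count changes if every AE has a grade.

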1.4 BENEFIT - RISK ASSESSMENT

Trial 1280.4, a Phase Ib/II open-label, randomised study of xentuzumab in combination with exemestane and everolimus versus exemestane and everolimus alone in women with locally advanced or metastatic breast cancer (HR+/HER2- mBC) was terminated early in October 2016 due to a Data Monitoring Committee (DMC) recommendation and an observed preliminary HR for PFS of 1.38 (95% CI: 0.687-2.778). Although this indicated low probability to achieve the desired HR at the time of primary analysis, a subgroup analysis of PFS in the pre-specified subgroup of patients with non-visceral disease derived clear benefit as described in [section 1.3](#).

The safety profile of xentuzumab monotherapy is tolerable. In combination with everolimus and exemestane the safety profile of the combination is largely dominated by side effects observed for the backbone therapy. To date the only expected serious adverse reaction identified for xentuzumab are infusion-related reactions mostly CTCAE grade 1 and 2 ([c01690707](#)).

Addition of xentuzumab 1000 mg to established backbone treatment in Phase Ib/II trial 1280.4 did not add any safety concerns, however provided increased efficacy to a subgroup of female HR+/HER2- metastatic breast cancer patients with non-visceral disease. These patients frequently suffer from bone and lymph node metastases and there is a sound scientific rationale supporting the antitumour activity of xentuzumab in this patient population (see [Section 1.1](#)). Therefore further assessment of the observed preliminary treatment effect in patients with HR+/HER2- mBC without visceral disease is warranted in a large confirmatory trial. To safeguard patients in this proposed Phase II, a DMC will continuously monitor patients' safety as outlined in [Section 8.7](#). The benefit risk is considered positive.

Although rare, a potential for drug-induced liver injury (DILI) is under constant surveillance by sponsors and regulators. Therefore, this trial requires timely detection, evaluation, and follow-up of laboratory alterations in selected liver laboratory parameters to ensure patients' safety, see also [Section 5.2.6](#), adverse events of special interest.

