4.2.1.2 Emergency procedures

There are no special emergency procedures to be followed that are specific for this protocol.

Precaution should be taken to avoid extravasation of xentuzumab/placebo. Patients should be asked to report any pain or burning at the site of injection immediately. If extravasation is suspected the infusion should be stopped immediately.

To date the only expected serious adverse reactions identified for xentuzumab are infusion-related reactions observed in patients who received xentuzumab treatment ([c01690707](#)).

Xentuzumab/placebo infusion should always be administered under close supervision of a medically qualified staff member with immediate availability of appropriate resuscitation facilities.

Infusion reactions may occur during xentuzumab/placebo infusions and include pyrexia, chills, rigors, dyspnoea, urticaria, bronchospasm, hypotension and hypertension. A one hour observation period is recommended following each infusion. If there is no infusion reaction during the first treatment cycle, the observation period following xentuzumab/placebo infusions may be adjusted at the discretion of the investigator. Mild to moderate infusion reactions may be managed with a slower infusion rate and prophylactic antihistamines for subsequent dosing. Severe reactions require immediate and

permanent discontinuation of infusion (see [Table 4.2.1.2: 1](#)).

The infusion reactions should be treated symptomatically as judged clinically relevant by the investigator. For symptomatic treatment of infusion reactions: hydrocortisone, antihistamines such as chlorphenamine accompanied by an antipyretic/analgesic and/or a bronchodilator is recommended. The infusion duration may be extended to over one hour and up to a maximum of three hours, see [Section 4.1.4](#).

Table 4.2.1.2: 1 Infusion reaction management

Infusion reaction grade	Description of event	Management

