4.4 MANAGEMENT OF EXPECTED ADVERSE EVENTS

To date the only expected adverse events for xentuzumab are infusion related reactions, which will be graded according to CTCAE version 5.0 ([R18-1357](#)) and treated following standard of care or local guidance. Guidance is also provided in [Table 4.2.1.2: 1](#). Immune responses to the xentuzumab mAb will be assessed measuring anti-drug antibody levels during the trial.

However, in trial 1280.4 which was utilizing combination treatment with xentuzumab/everolimus and exemestane, the following AEs were reported in >20% of the patients: Diarrhoea, stomatitis, mucosal inflammation, rash, asthenia, nausea, cough, decreased appetite, fatigue, hyperglycemia, anaemia, neutropenia, vomiting, thrombocytopenia and increased ALT.

Proactive side effect management is crucial to maintain patients on long-term therapy and supportive measures for management of adverse events should be started as early as possible after onset of symptoms. Patients should be advised to report AEs promptly so that appropriate treatment can be initiated.

The following recommendations (as well as those in [Appendix 10.2](#)) should be followed unless institutional guidelines are available and are implemented based on the investigator's judgement. Side effects observed with everolimus and /or exemestane treatment should be managed in accordance with their current SmPC/PI.

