- Patients with related xentuzumab/placebo SAEs
- Patients with related everolimus SAEs
- Patients with related exemestane SAEs
- Patients with other significant AEs, defined as serious and non-serious AEs that lead to dose reduction or permanent discontinuation of any study medication
- Patients with AEs leading to death (no CTCAE grade required)
- Patients with AEs leading to discontinuation of xentuzumab/placebo
- Patients with AEs leading to discontinuation of everolimus
- Patients with AEs leading to discontinuation of exemestane
- Patients with AEs leading to dose reduction of everolimus
- Patients with AEs leading to dose interruption of xentuzumab/placebo
- Patients with AEs of Special Interest (refer to Section 5.2.6.1 of the CTP)

In addition some AEs are considered to be of particular importance and special search categories (SSC) of groupings of PTs based on Standardised MedDRA Queries (SMQ), BI customised MedDRA Queries (BIcMQ) or MedDRA High Level Terms (HLT) are defined at the project level, the latest version of which will be used. Details of the current version are provided in the Table 7.8.1: 1 below.

SSCs summaries of patients with AEs and related AEs by treatment, highest CTCAE grade, grouped term and PT will be produced. Similar summaries will be produced for the BIcMQ SARS-COV-2-infections.

Table 7.8.1: 1 Overview of Special Search Categories

Grouped term	Groupings
Hepatic impairment	SMQ: Drug related hepatic disorders – comprehensive search
Hyperglycaemia narrow	SMQ: Hyperglycaemia / new onset diabetes mellitus (narrow terms only)
Infusion related reaction	SMQ: Hypersensitivity
Non-infectious pneumonitis	SMQ: Interstitial lung disease (narrow terms only)
Renal insufficiency	SMQ: Acute renal failure, SMQ: Proteinuria, HLT: Glomerulonephritis and nephrotic syndrome
Weight loss	BIcMQ: Weight loss
Neutropenia	SMQ: Haematopoietic leukopenia (narrow terms only)
Stomatitis	BIcMQ: Gastrointestinal mucositis (subsearch1: Stomatitis)

Table 7.8.1: 1 Overview of Special Search Categories (cont.)

Grouped term	Groupings
Asthenia	MedDRA PTs of Asthenia, Fatigue, Lethargy, Malaise, and Decreased activity
Haemorrhage	SMQ: Haemorrhage laboratory terms (narrow terms only), SMQ: Haemorrhage terms (excl. laboratory terms)
Anemia	SMQ: Haematopoietic erythropenia
Thrombocytopenia	SMQ: Haematopoietic thrombocytopenia (narrow terms only)
Thromboembolism	SMQ: Embolic and thrombotic, vessel type unspecified and mixed arterial and venous

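### The SAP's 'Infusion related reaction' row is an untimed hypersensitivity query, so it can count events far from, or after the end of, xentuzumab/placebo infusions

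*SAP*

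**What the plan says.** SAP 7.8.1 plans special search categories, which are groups of preferred terms set at project level. Each is tabulated by arm, highest CTCAE grade, group and preferred term, once for all events and once for related events. In Table 7.8.1: 1 the row named *Infusion related reaction* has one entry: "SMQ: Hypersensitivity". No timing rule is attached.

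The general counting rule in the same section is that "all AEs with an onset between first drug intake and last drug intake + REP (42 days) will be assigned to the randomised treatment". SAP 6.1 takes the last dose as the latest one across the separate components. The overall AE summary also carries an item described as "worst CTCAE grade and infusion related reaction response"; the visible text does not define it.

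Protocol 4.2.1.2 says: "Infusion reactions may occur during xentuzumab/placebo infusions and include pyrexia, chills, rigors, dyspnoea, urticaria, bronchospasm, hypotension and hypertension". It recommends an hour of observation after each infusion. It also says: "To date the only expected serious adverse reactions identified for xentuzumab are infusion-related reactions observed in patients who received xentuzumab treatment".

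**The concern.** A reader of the safety report will take the row at its name and use it to compare the arms on the one serious reaction expected from xentuzumab. What the row delivers is a list of allergy-type terms collected over the whole on-treatment period. Two things could follow. Events with no connection to an infusion could enter both arms and pull the arm ratio towards 1. Signs that the protocol regards as infusion reactions could also be left out, if the query does not contain them. At stake is how clearly the drug-specific safety signal can be read. No test, error rate or expansion decision depends on it.

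**Working it through.** The documents attach no rate, sample size or power to this category, so there is no stated figure to reproduce. The check sets the texts side by side and then adds an illustration on assumed inputs.

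**1. Timing.** Protocol 4.2.1.2 ties the reaction to the infusion and the hour after it. SAP 7.8.1 ties the row only to a list of terms, and a list of terms carries no timing. Infusions are weekly, so even for a patient who misses none, 6 of every 7 treatment days (86%) are not infusion days, yet an event on any of them qualifies.

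**2. Time after infusions stop.** The protocol flow chart footnote on treatment provides for patients who have discontinued xentuzumab/placebo but remain on everolimus/exemestane. Take a hypothetical patient:
- Last infusion at cycle 2 day 22, i.e. study day 28 + 22 = 50.
- Oral drugs to the end of cycle 20, i.e. day 20 × 28 = 560.
- On-treatment window closes at day 560 + 42 = 602.
- A hypersensitivity event up to 602 − 50 = 552 days after the last infusion still counts in the row.

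Hypersensitivity without an infusion is not far-fetched: protocol exclusion criterion 6 recognises it for any of the study drugs.

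**3. Coverage of terms.** Protocol 4.2.1.2 names pyrexia, chills and rigors among the signs. Neither document lists the terms in the query. Whether these signs are in it, and whether rash is in it, cannot be settled from the documents.

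**4. Illustration of size (all rates assumed).** Let b be the share of patients in each arm with an unrelated event in the category, q the true infusion-reaction rate on xentuzumab (zero on placebo), and s the share of true reactions that the query captures. Then the xentuzumab rate is 1 − (1 − b)(1 − s·q) and the placebo rate is b. The standard error of the difference is unpooled, with 40 patients per arm.

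| b | q | s | Xentuzumab vs placebo | Difference (SE), points | Ratio |
|---|---|---|---|---|---|
| 0% | 10% | 1 | 10% vs 0% | 10 (4.7) | not defined |
| 10% | 10% | 1 | 19% vs 10% | 9 (7.8) | 1.90 |
| 20% | 10% | 1 | 28% vs 20% | 8 (9.5) | 1.40 |
| 20% | 10% | 0.5 | 24% vs 20% | 4 (9.3) | 1.20 |
| 30% | 5% | 0.5 | 31.8% vs 30% | 1.8 (10.3) | 1.06 |
| 10% | 20% | 1 | 28% vs 10% | 18 (8.5) | 2.80 |

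Worked line: 1 − 0.80 × 0.90 = 0.28; SE = √(0.28 × 0.72/40 + 0.20 × 0.80/40) = 0.095.

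Over b = 10–30%, q = 5–20% and s = 0.5–1, the difference runs from 1.8 to 18 points and the ratio from 1.06 to 2.80. Background mainly affects the ratio and the precision. With full capture, q = 10% and b = 20%, the difference moves only from 10 to 8 points, but its standard error doubles from 4.7 to 9.5. The first row shows no distortion.

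**The case against.** A reader might infer that the row counts rashes from the backbone drugs and misses fever and chills, and so hides xentuzumab's reaction. The documents do not support that reading. The query's content is an outside term list. The rash figure in protocol 4.4, "the following AEs were reported in >20% of the patients: Diarrhoea, stomatitis, mucosal inflammation, rash", is for the triple combination; no backbone-only rate is given, although protocol 1.4 says that "the safety profile of the combination is largely dominated by side effects observed for the backbone therapy". An event reported as an infusion reaction may also be coded to one term that the query contains. Protocol 4.2.1.2 and its table grade the reaction as a single event, which points that way.

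Nor can much be made of this row lacking the narrow-terms limit seen in, for example, the non-infectious pneumonitis row. Several other rows lack it too, including hepatic impairment, renal insufficiency, anaemia and thromboembolism.

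The plan also has safeguards. All AEs, and those related to xentuzumab/placebo, are tabulated by grade, system organ class and preferred term. There are further tables for xentuzumab/placebo-related SAEs and for AEs leading to its discontinuation or interruption. The grouped row is itself split by preferred term, so a rash within it would show as a rash, and rash has its own row. The overall summary has an infusion-reaction item whose definition may stand in text not shown, so the lack of a visible definition is not a fault.

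All of this stands, and it limits the harm. It does not tie this row to infusion timing. A preferred-term split cannot separate an infusion-day event from a later one with the same term. The related-event version of the grouped table names no compound, so an event attributed to everolimus may qualify.

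**Conclusion.** The point holds in a limited form. As written, the row named for infusion reactions is an untimed hypersensitivity count. It departs from the protocol's own description of the reaction and can include events far from any infusion or after infusions have ended. This rests only on the table entry, the 42-day rule, the latest-dose rule and the provision for continuing the oral drugs alone. It also assumes that the query holds at least one term that can arise without an infusion.

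The size is unknown. The figures in the illustration rest wholly on assumed rates and include the case of no distortion. It is not shown that rash is counted, that fever or chills are missed, or that a signal would be hidden once the other tables are read. The analysis is descriptive, so no inferential result changes.

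**What to change.** - Keep the project-level query, but report it in this trial under the name *Hypersensitivity*.
- Add a trial-level *Infusion related reaction* row, by grade and preferred term. It should hold events that the investigator reported as infusion reactions, plus events in the query or with the signs in protocol 4.2.1.2 whose onset falls in a pre-specified window around a xentuzumab/placebo infusion. The infusion day could be the main window, for example, with the day after added as a sensitivity analysis.
- State how this row relates to the infusion-reaction item in the overall AE summary, and whether pyrexia, chills and rigors are captured.

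The data should already exist. Protocol 8.3.1 makes AE onset date mandatory and lists visit dates among the source data, and protocol 4.1.5.1 has infusions given at the site. The cost is a merge of onset dates with infusion dates and one row that departs from the project-level standard. Some unrelated events will still be counted: with weekly infusions the infusion day covers 1/7 (14%) of days, and adding the day after makes it 2/7 (29%).
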